4.1.2. Baseline Definition

For all endpoints (except as noted in baseline definitions) the baseline value will be the latest pre-dose assessment with a non-missing value, including those from unscheduled visits. If time is not collected, Day 1 assessments are assumed to be taken prior to first dose and used as baseline.

For ECG and/or Vital Signs analyses, if the last, non-missing pre-dose values is measured in triplicate, then the subject level baseline is defined as the mean of the triplicate baseline assessments.

Blood pressure and pulse will be measured in triplicate before dosing, single measurements after dosing. Single temperature and respiratory rate measurements will be measured at all time points. When measurement is repeated at the same time point then the mean will be used.

Unless otherwise stated, if baseline data is missing no derivation will be performed and baseline will be set to missing.

Baseline of serum creatinine is defined as the mean of all pre-dose values, from screening to Day 1 pre-dose assessment.

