Brief physical examination		X 	X 		X 	X	X	X	X	X		An interim symptom-targeted brief physical examination.  Within 1 h before dosing and at 24 and 72 h after dosing.
Vital signs	X	X 	X 	X 	X 	X	X	X	X	X		Blood pressure and heart rate in triplicate before dosing, and single measurements after dosing. Respiratory rate and temperature, single measurements at all time points.  Within 1 h before dosing and at 24, 48 and 72 h after dosing.
COVID-19 test	X											Using a PCR or antigen test approved by the country regulatory authorities. Test can be performed before Day –1 if required before admission for inpatient stay.
Drug, alcohol, and cotinine screen	X											As per standard local practice.
Safety 12-lead ECG	X	X 	X 	X 						X		In triplicate before dosing; single measurements after dosing.  Within 1 h before dosing and at 24 and 48 h after dosing.
Pregnancy test	X									X	X	Serum or urine. WOCBP only.
Clinical chemistry, haematology and urinalysis		X 	X 			X	X 	X 	X 	X	X	 Within 1 h before and at 24 and 72 h after dosing.  If results on Day 15 are within normal range, Day 29 and 43 tests are not required, and the next required time point is Day 64. If results on Day 15 are out of normal range, test should be repeated on Day 29; if results are still out of range on Day 29, test should be repeated on Day 43.
Urine ACR		X 	X 			X		X		X		 Within 1 h before and at 24 h after dosing.
C3, C4, hs-CRP, p-ANCA, c-ANCA		X 										 Within 1 h before dosing. Post-dose sample to be taken only if the investigator considered there was an event of vascular inflammation

CONFIDENTIAL

219239  
Protocol

Procedure	Day										Early withdrawal	Notes
CCI												
	Refer to Table 3 for acceptable time windows											
Coagulation Panel (PT, INR, APTT)		X 										 Within 1 h before dosing.
Randomization		X										
CCI dose of bepirovirsen		CCI									CCI	
CCI												
Assessment of injection site		X 	X 	X 	X 	X	X	X	X	X	X	 Within 1 h before dosing and at 24, 48 and 72 h after dosing.
CCI												

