4.5.2.4. Vital Signs

Summary statistics for absolute values and change from baseline (by each time point and treatment group) in temperature, pulse rate, respiratory rate, systolic blood pressure (SBP), diastolic blood pressure (DBP) will be provided.

Also, by-treatment summaries of grade increase in temperature, SBP and DBP will be provided separately. These summaries will display the number and percentage of participants with any grade increase, increase to Grade 2, increase to Grade 3 and increase to Grade 4 (for temperature only), for worst case post-baseline only. The summaries will be produced for worst case post baseline only. The DAIDS grading system Version 2.1 [National Institute of Allergy and Infectious Diseases. Division of AIDS, 2017], will be used for grading: The grade definition for temperature is: Grade 1 (38.0°C – <38.6°C),

Grade 2 ($38.6^{\circ}\text{C} - <39.3^{\circ}\text{C}$), Grade 3 ($39.3^{\circ}\text{C} - <40.0^{\circ}\text{C}$), Grade 4 ($\geq 40.0^{\circ}\text{C}$). The grade definition for SBP is Grade 1 (140-159), Grade 2 (160-179), Grade 3 (≥ 180). The grade definition for DBP is Grade 1 (90-99), Grade 2 (100-109), Grade 3 (≥ 110). DAIDs does not include a Grade 0, please refer to the OPS for instruction on how to present values that don't meet the criteria for Grade 1+. Participants with missing baseline values are assumed to have a normal baseline value.

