6.2.4. Multiple measurements at One Analysis Time Point

Mean of the measurements (e.g., ECG) will be calculated and used in any derivation of summary statistics but if listed, all data will be presented.

If there are two values within a time window the value closest to the target time for that window will be used. If values are the same distance from the target, then the mean will be taken.

Participants having both High and Low values for Normal Ranges at any post-baseline visit (including post-baseline unscheduled assessments) for safety parameters will be counted in both the High and Low categories of “Any visit post-baseline” row of related summary tables.

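### The SAP does not say which post-baseline values feed its graded worst-case safety tables, and its repeat-measurement rules, read literally, let a recheck lower the tabulated worst grade

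*SAP*

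**What the plan says.** SAP 4.1.2 sits under the baseline heading, but its vital-signs paragraph covers both sides of dosing: "Blood pressure and pulse will be measured in triplicate before dosing, single measurements after dosing". That agrees with the protocol's schedule of activities: "Blood pressure and heart rate in triplicate before dosing, and single measurements after dosing". The same SAP paragraph then gives the repeat rule, "When measurement is repeated at the same time point then the mean will be used", with no restriction to pre-dose readings.

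SAP 6.2.4 has two further rules:

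- Averaging: "Mean of the measurements (e.g., ECG) will be calculated and used in any derivation of summary statistics", with every value kept only where data are listed.
- Selection: "If there are two values within a time window the value closest to the target time for that window will be used", with the mean used when two values are equally distant.

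One sentence in 6.2.4 brings in unscheduled values. It begins "Participants having both High and Low values for Normal Ranges at any post-baseline visit (including post-baseline unscheduled assessments" and governs the High and Low normal-range counts.

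The graded tables are defined elsewhere. For the vital-sign grades (temperature, systolic and diastolic pressure), SAP 4.5.2.4 says: "The summaries will be produced for worst case post baseline only". SAP 4.5.2.2 plans maximum-grade and shift tables for gradable laboratory tests. It also plans summaries of increases to Grade 3 or above for platelets, ALT, AST, WBC, total bilirubin, creatinine and ACR, and plots of maximum ALT and bilirubin. Neither section says whether these use all recorded values or one reduced value per time point.

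**The concern.** Averaging suits three planned readings taken together. It does not suit a single post-dose value followed by a recheck, because the recheck often exists only because the first value was abnormal. For laboratory tests the protocol says so. Section 7.1.2 calls for a platelet recheck below the lower limit of normal, 7.1.3 for confirmation of renal findings, 8.3.5 for repeats of clinically significant abnormal results, and Appendix 6 for repeat liver chemistries after ALT of at least 3 times the upper limit.

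A worst-case table should show the worst valid value that occurred. If the reduced value feeds it, a participant's grade can fall because someone checked again, and more diligent rechecking gives a cleaner table. The silence also means that two programmers could produce different graded tables from the same SAP.

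**Working it through.** The plan states no figure to reproduce. The check has three steps.

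**1. Direction.** For two values, the mean cannot exceed the larger, and a selected value is one of the two. Where high is bad, either rule gives a result at or below the true worst case. Where low is bad (platelets, for example), the result is at or above it. The shift is toward normal or zero, never the other way.

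**2. Worked pairs**, using the SAP 4.5.2.4 limits (systolic Grade 1 140-159, Grade 2 160-179, Grade 3 from 180; temperature Grade 1 from 38.0, Grade 2 from 38.6 °C). The readings are illustrative.

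| First, repeat | Grade, all values | Mean | Grade from mean | Grade if only repeat kept |
|---|---|---|---|---|
| SBP 182, 150 | 3 | (182+150)/2 = 166 | 2 | 1 |
| SBP 164, 138 | 2 | (164+138)/2 = 151 | 1 | none |
| SBP 146, 130 | 1 | (146+130)/2 = 138 | none | none |
| SBP 168, 156 | 2 | (168+156)/2 = 162 | 2 | 1 |
| Temp 38.8, 37.4 | 2 | (38.8+37.4)/2 = 38.1 | 1 | none |

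The fourth pair shows that averaging can also leave the grade unchanged. A mean such as 159.5 would fall between the integer bands for Grades 1 and 2.

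For the selection rule, protocol Table 3 (adopted by SAP 6.2.3) allows 3 days either side from Day 29 onwards. Suppose the Day 64 sample is drawn on Day 62 with low platelets and rechecked on Day 63. The distances are |62-64| = 2 and |63-64| = 1, so the recheck is kept. Had the first sample been drawn on Day 64, it would be kept and nothing would be lost.

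**3. Size under assumptions.** 400,000 participants were simulated, each with eight post-dose systolic readings (24, 48 and 72 h plus five later visits, counted from protocol Table 2). Only the limit of 140 and that count come from the documents. The overall mean, the between- and within-person SDs and the repeat frequency are assumed. Anyone whose own mean reached 140 was reset to the overall mean, since participants are healthy. A reading of 140 or more was repeated once, always or half the time. The selection rule was taken to keep either value with equal chance. Entries are the percentage of participants with any Grade 1 or higher value. In brackets is the loss, 1 - (rule / all values).

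| Mean / between SD / within SD | High readings repeated | All values | Mean rule | Closest rule |
|---|---|---|---|---|
| 118 / 9 / 6 | 50% | 7.52 | 5.46 (27%) | 6.41 (15%) |
| 118 / 9 / 6 | 100% | 7.52 | 2.89 (62%) | 5.15 (32%) |
| 118 / 9 / 8 | 50% | 14.31 | 10.29 (28%) | 12.15 (15%) |
| 118 / 9 / 8 | 100% | 14.31 | 5.18 (64%) | 9.59 (33%) |
| 120 / 10 / 8 | 50% | 19.71 | 14.78 (25%) | 17.07 (13%) |
| 120 / 10 / 8 | 100% | 19.71 | 8.47 (57%) | 13.91 (29%) |
| 120 / 10 / 10 | 50% | 28.91 | 21.72 (25%) | 25.02 (13%) |
| 120 / 10 / 10 | 100% | 28.91 | 12.42 (57%) | 20.29 (30%) |

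Grade 2 or higher occurred in under 1% of participants in every setting, so in healthy volunteers the effect falls mainly on Grade 1 counts. The simulation counts any grade, whereas the SAP tabulates increases from baseline grade.

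**The case against.** The strongest reply is that the SAP keeps summary statistics apart from category counts. SAP 6.1.2 spells out the former as n, mean, SD, median, minimum and maximum, and 4.5.2.2 and 4.5.2.4 introduce the grade tables separately as numbers and percentages. On that usage the averaging sentence in 6.2.4 need not reach a grade table. This stands for that sentence. It does not dispose of the repeat rule in 4.1.2 or the selection rule in 6.2.4, neither of which is tied to summary statistics.

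A reader might infer more than the documents support:

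- *All worst-case tables are biased.* High/Low rows already count unscheduled values. For graded tables the SAP is silent, so dilution is a literal reading and not a stated rule.
- *Heart rate and ECG are affected too.* Neither has a visible graded table, and SAP 4.5.2.5 limits ECG averaging to triplicates.
- *Every repeat follows an abnormal value.* No repeat trigger is given for vital signs, so that part is inference. Protocol section 8 also allows repeat samples for technical reasons.
- *The two rules contradict each other.* One can be read as covering repeats at the same time point, the other different times within one window.

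Other safeguards are real. Listings keep all data, clinically significant abnormalities are adverse events, and monitoring events and events of special interest are reported separately. The stated safety endpoint is change from baseline at each time point, not worst grade. The Output and Programming Specification, which is not available here, may add detail.

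**Conclusion.** The point holds as a gap with a known direction. The SAP does not define the source values for its DAIDS worst-case, maximum-grade, shift and Grade 3+ tables, and two of its rules, followed literally, can lower the tabulated worst grade for systolic and diastolic pressure, temperature and graded laboratory tests. They cannot raise it.

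The documents do not fix the size. On the assumed inputs, the loss of participants with any graded systolic value runs from about 13% (closest rule, half of high readings repeated) to about 64% (mean rule, all repeated). The upper end is close to a ceiling, and the loss is nil if nothing is repeated or if the programmers use all values anyway. The primary and secondary pharmacokinetic analyses are untouched. The text is worth correcting because the graded tables carry the laboratory parameters of most safety interest and the change is small.

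**What to change.** - In SAP 4.1.2 and 6.2.4, limit the mean and closest-to-target rules to planned triplicates and by-visit summary statistics.
- In 6.2.4, with a cross-reference from 4.5.2.2 and 4.5.2.4, state that all worst-case, maximum-grade, shift, Grade 3+ and maximum ALT/bilirubin displays use every valid post-baseline value, whether scheduled, repeat or unscheduled. Exclude samples documented as uninterpretable, such as clumped platelets.

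The cost is a few sentences and a programming note. Worst-case counts will look less favourable than under the literal rules; in the simulation above the difference was not always slight. Participants with more repeats also have more chances to reach a high value, which a footnote to the tables should acknowledge.

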4.1.3. Plasma bepirovirsen concentration-time data Analysis

Plasma bepirovirsen concentration-time data will be analysed by the Clinical Pharmacology Modelling & Simulation department within GSK, using noncompartmental methods with Phoenix WinNonlin version 8.0 or higher. Statistical analysis will be performed by Biostatistics, GSK. Calculations will be based on the actual sampling times recorded during the study.

CCI

CCI

4.2.3. Supplemental estimands

A supplemental estimand to the primary objective assessing the impact of participants who were unable to take the complete dose. The estimand will be the same as the primary estimand except for the intercurrent event of incomplete dosing (participants who did not take CCI vials) which will now be considered using a treatment policy strategy.

CCI

CCI

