#### Primary estimand

The primary interest is to estimate the relative bioavailability, measured by Cmax and AUC(0-inf), following a **CCI** of bepirovirsen via PFS SSD versus a vial in healthy adult participants.

The primary PK estimands are described by the following attributes:

- Population:
 

Healthy male and female participants aged 18 to 55 years.
- Treatment Condition:
 

**CCI** of bepirovirsen injection administered via PFS SSD versus **CCI** of bepirovirsen administered via a vial.

**CONFIDENTIAL**219239  
Protocol

- Variables:

AUC(0-inf) and Cmax.

- Summary measure:

Ratio of geometric means of PFS SSD versus vials for Cmax and AUC(0-inf).

- Intercurrent Events:

Use of prohibited medication. This intercurrent event is not expected to impact the PK of bepirovirsen so a treatment policy strategy will be used, and the individual PK concentrations after the occurrence of the intercurrent event will still be included in the PK analysis.

Participants who did not receive **CCI** the injections and had an incomplete or erroneous dosing. A principal stratum strategy policy will be used, where the strata of interest is the group of participants who are able to receive the complete dose.

A supplemental estimand will also be analyzed as per the primary estimand, except for the intercurrent event of incomplete dosing will use a treatment policy strategy.

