## **Secondary estimand(s)**

The secondary interest is to estimate the relative bioavailability, measured by Cmax and AUC(0-inf):

1. Following a **CCI** of bepirovirsen via PFS SSD versus self-administration of a single dose of bepirovirsen with HCP training
2. Following a **CCI** of bepirovirsen via PFS SSD versus self-administration of a single dose of bepirovirsen with no HCP training.

The secondary PK estimands are described by the following attributes:

- Population:

Healthy male and female participants aged 18 to 55 years.

- Treatment condition:

**CCI** dose of bepirovirsen administered via PFS SSD versus self-administration of a single dose of bepirovirsen with HCP training.

**CCI** dose of bepirovirsen administered via PFS SSD versus self-administration of a single dose of bepirovirsen with no HCP training.

**CONFIDENTIAL**219239  
Protocol

- Variables:

AUC(0-inf) and Cmax.

- Summary measure:

Ratio of geometric means of PFS SSD versus self-administration with HCP training and with no HCP training for Cmax and AUC(0-inf).

- Intercurrent Events:

Use of prohibited medication. This intercurrent event is not expected to impact the PK of bepirovirsen so a treatment policy strategy will be used, and the individual PK concentrations after the occurrence of the intercurrent event will still be included in the PK analysis.

Participants who did not receive **CCI** the injections and had an incomplete or erroneous dosing. A principal stratum strategy policy will be used, where the strata of interest is the group of participants who are able to receive the complete dose.

Supplemental estimands will also be analysed as per the secondary estimand, except for the intercurrent event of incomplete dosing will use a treatment policy strategy.

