### 6.1. Study intervention(s) administered

**Table 5** Study Intervention(s) Administered

Intervention Label	Open Label	Open Label
Intervention Name	Bepirovirsen, (GSK3228836)	Bepirovirsen, (GSK3228836)
Intervention Description	Bepirovirsen solution for injection, CCI mg/mL packaged in a vial. CCI ██████████ required to deliver CCI mg dose.	Bepirovirsen solution for injection, CCI mg/mL packaged in a PFS fitted with a PFS SSD. CCI ██████████ required to deliver CCI mg dose.
Type	Drug	Drug
Dose Formulation	Solution for injection	Solution for injection
Unit Dose Strength(s)	CCI mg/mL	CCI mg/mL
Dosage Level(s)	CCI mg	CCI mg
Route of Administration	SC Injection	SC Injection
Use	Experimental	Experimental
IMP and NIMP/AxMP.	IMP	IMP
Sourcing	Supplied by GSK	Supplied by GSK
Packaging and Labeling	Study intervention will be provided in a carton with an insert. Each carton will be labeled as required per country requirement.	Study intervention will be provided in carton with an insert. Each carton will be labeled as required per country requirement.

Bepirovirsen Solution for Injection, **CCI** mg/mL, is a clear, **CCI** **██████████** solution, essentially free from visible particles. Bepirovirsen vial is presented as a 1 mL nominal fill volume of Bepirovirsen Solution for Injection **CCI** mg/mL in a **CCI** mL clear glass vial, closed with a **CCI** **██████████** rubber stopper and sealed with aluminium overseal with removeable plastic cap.

The drug product is administered as **CCI** SC injections to deliver the clinical dose of **CCI** mg. It is recommended to use 27G thin-wall needles or 25G regular-walled needles for injection.

The PFS SSD is a medical device and is described in Section [6.1.1](#).

**CONFIDENTIAL**219239  
Protocol

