### **8.4.8. Medical device deficiencies**

Medical devices (PFS SSD) are being provided for use in this study as the study intervention from Groups 2 to 4. To fulfill regulatory reporting obligations worldwide, the investigator is responsible for the detection and documentation of events meeting the definitions of device deficiency that occur during the study with such devices.

The definition of a medical device deficiency can be found in Section [10.6](#).

NOTE: Deficiencies fulfilling the definition of an AE/SAE will follow the processes outlined in Section [10.6](#) of the protocol.

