1.2. Study Design

Overview of Study Design and Key Features	
Design Features	
This is a Phase 1, open-label, randomized study to investigate SC bepirovirsen when delivered via SC injection from a vial and PFS SSD in healthy adult participants. The study will assess relative bioavailability, safety, and tolerability, as well as the usability of the PFS SSD for self-administration.
 
A total of approximately CCI participants will each complete a single study session, in a parallel design, and will take up to CCI weeks to complete the study.
 
Participants will be screened within 28 days before dosing. They will attend the clinical unit the day before dosing (Day -1) and will remain inpatient until 2 days after dosing (Day 3). Participants will return for outpatient visits on Days CCI
 
Blood samples will be taken to measure levels of bepirovirsen and ADAs against bepirovirsen, and safety and tolerability will be assessed from before dosing and until the final visit. The observing HCP and participants in Groups 3 and 4 will complete questionnaires, respectively, during and after dosing, to assess usability of the PFS SSD for self-administration. Blood samples will also be taken for biomarker analysis before dosing and up to 48h after dosing.

Study intervention	CCI

Overview of Study Design and Key Features	
	CCI
Study intervention Assignment	Participants will be randomized in a ratio of 3:3:2:2 to one of the four treatment groups. The randomization will be stratified by body weight (CCI [REDACTED]). The site of injection will be randomized in a 1:1:1 ratio to upper arm, abdomen, and thigh in Groups 1 and 2, and in a 1:1 ratio to abdomen or thigh in Groups 3 and 4.
Interim Analysis	CCI

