4.3.1.4. Supplemental estimands

[figure not shown]
A supplemental estimand to the secondary objective assessing the impact of participants who were unable to take the complete dose will be considered as described in Section 4.2.3.

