4.7. Changes to Protocol Defined Analyses

There were no changes or deviations to the originally planned statistical analysis specified in the protocol. (Dated : [26th July 2023]).

CCI

A large black rectangular redaction box covers the majority of the page content below the 'CCI' label.

CCI

CCI

To assess the secondary objectives of estimating the relative bioavailability of Group 2 compared to Groups 3 and 4, approximately CCI subjects will be randomized into Groups 3 and 4 (approximately CCI per arm). This will provide the same number of subjects in the applicable sites of administration (thigh and abdomen) compared to Groups 1 and 2.

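### Does the word vials in SAP 4.2.3 stop the supplemental estimands from covering incomplete dosing in the prefilled-syringe groups?

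*SAP*

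**What the plan says.** In Protocol Section 3 the intercurrent event for the primary estimand concerns participants who did not receive a redacted quantity of "the injections and had an incomplete or erroneous dosing". The main estimand uses a principal stratum strategy. The supplemental estimand uses treatment policy for incomplete dosing. The secondary estimands repeat this: "Supplemental estimands will also be analysed as per the secondary estimand, except for the intercurrent event of incomplete dosing" moves to treatment policy.

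SAP 4.2.3 gives the purpose as assessing the impact of participants who could not take their full dose. It then says the estimand is the same as the primary one "except for the intercurrent event of incomplete dosing (participants who did not take CCI vials", and closes the parenthesis. SAP 4.3.1.4 gives the same purpose for the secondary objective and says it "will be considered as described in Section 4.2.3".

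On presentations, Table 5 in Protocol 6.1 lists one product in a vial and one "packaged in a PFS fitted with a PFS SSD". Protocol 8.4.8 says: "Medical devices (PFS SSD) are being provided for use in this study as the study intervention from Groups 2 to 4". That leaves Group 1 as the vial group. On allocation, SAP 1.2 says: "Participants will be randomized in a ratio of 3:3:2:2 to one of the four treatment groups". On departures from the protocol, SAP 4.7 says: "There were no changes or deviations to the originally planned statistical analysis specified in the protocol".

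**The concern.** Most participants never handle a vial, so an event defined by vials seems to miss them. If it applies only to vial users, a Group 1 participant who missed a vial enters the supplemental analysis of the primary comparison, while a Group 2 participant who missed a syringe stays out. In the secondary comparisons nobody's handling changes, so the supplemental result only repeats the main one.

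That would matter. Self-administration, especially without training, is where the effect of incomplete dosing on exposure is of most interest. The visible SAP offers little else on it: study intervention compliance (6.1.5) is marked not applicable, and important deviations (6.1.3) are summarized and listed without their effect on exposure.

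**Working it through.** **Who uses vials.** With 3:3:2:2 allocation and Group 1 as the vial group:
- all randomized: 3/10 use vials and 7/10 use the PFS SSD;
- primary comparison (Group 1 with Group 2): 3/6 use vials;
- secondary comparisons (Group 2 with Groups 3 and 4): nobody uses vials.

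The term therefore does fit the syringe groups badly.

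**What each reading does.** The required number of units is redacted. Two and three were tried as assumptions and gave the same pattern. The table shows whether the event is met. Group 1 participants who complete dosing do not meet it under any reading.

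| Reading of the event | Group 1, incomplete | Groups 2–4, incomplete | Groups 2–4, complete |
|---|---|---|---|
| Vial users only | yes | no | no |
| Fully literal (took fewer than the required vials) | yes | yes | yes |
| Protocol (did not receive the injections) | yes | yes | no |

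Only the first reading produces the feared result. Under the fully literal reading, complete syringe dosers also meet the event. Treatment policy changes nothing for them, so the estimates equal those under the protocol's definition. The only oddity would be an event count of 100% in Groups 2 to 4.

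**What the text supports.** The vial-users-only reading lets a parenthesis override four other places:
- the main clause of SAP 4.2.3, which speaks of the complete dose;
- SAP 4.3.1.4, which governs the secondary comparisons, repeats that phrase and never mentions vials;
- the protocol's secondary estimands, which apply treatment policy to incomplete dosing in comparisons made up only of PFS SSD groups;
- SAP 4.7, which declares no departure from the protocol.

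It also makes the secondary supplemental analysis pointless by construction.

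**Size under the disputed reading.** The documents give no rate of incomplete dosing and no share of dose delivered, so both are assumed. Let p be the fraction incompletely dosed and d the share delivered, with dose-proportional exposure and a true ratio of 1.00. A group that includes its cases has geometric mean d^p relative to full dosing.
- Primary, same p in both groups, cases admitted only in the vial group: PFS SSD/vial = d^(−p). For d = 0.5 this is 1.035 (p = 0.05) or 1.072 (p = 0.10). For d = 0.75 it is 1.014 or 1.029. Admitting cases in both groups gives 1.00.
- Secondary, cases in the self-administration group only: self/HCP under treatment policy = d^p. This is 0.966 or 0.933 for d = 0.5, and 0.986 or 0.972 for d = 0.75. The vial-users-only reading would give 1.00.

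These figures describe only the reading that the text does not support.

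**Dependence on the PK sets.** The primary-comparison figures also need incomplete Group 1 dosers to enter the analysis. In SAP Section 3 the PK concentration set requires receipt of a redacted quantity of the injections, and the PK parameter set is drawn from it. SAP 4.1.1 uses the PK set for PK analyses. If the hidden word means all (an assumption), incomplete dosers in every group, vial users included, are outside that set unless redacted text names another population. The asymmetry would then not arise at all.

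**The case for a change.** The strongest reply is that a programming definition should not need rescuing by its context. The parenthesis is the most specific statement of the event in the visible SAP, and neither direct reading of it picks out incomplete dosing in the syringe groups: one finds nobody, the other finds everybody. The intended event is reached only by setting the gloss aside. The correction would be cheap, and so would a sentence naming the supplemental population.

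What stands is that the term is wrong for Groups 2 to 4 as far as the visible text shows, and that it departs from the protocol's injections. A flag or count programmed from the parenthesis alone would be misleading.

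What does not stand is that the results would go wrong. The surrounding sentences say what the event is, the protocol says it again for each comparison, and the fully literal reading gives the same estimates. The words just before vials are redacted and could name the PFS SSD, in which case nothing is left. The population may likewise be stated in the redacted parts of SAP 4.2 and 4.3, so its absence from view is not evidence of a gap. Whether erroneous dosing should also move to treatment policy is not a discrepancy either: the supplemental estimands in both documents name only incomplete dosing.

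**Conclusion.** This is a clerical slip: vials stands where the protocol has injections. It does not call for a change to the plan. The main estimands are unaffected. For the supplemental estimands, the context and the protocol give the intended event, and the fully literal reading gives the same estimates, so the shift from the wording is nil under either. Ratios of 1.014 to 1.072 (primary) or 0.933 to 0.986 (secondary) would be at stake only if the parenthesis overrode its own sentence, SAP 4.3.1.4 and the protocol, and only under assumed rates of 5% to 10% and assumed dose shares of one half to three quarters. All dosing takes place at the site, with self-administration supervised (Protocol 6.5), so cases should be few. With none, every reading agrees.

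The conclusion assumes that the analyst reads SAP 4.2.3 with the protocol estimand it implements, and that the redacted text does not restrict the event to vial users.
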